8.2.3.5 Quality of Life analysis

See chapter 10.

8.2.4 Pre-planned sensitivity or exploratory analyses

8.2.4.1 Pre-planned sensitivity analyses

If the percentage of patients ineligible and/or who did not start allocated treatment is superior to 10%, sensitivity overall survival and progression-free survival analyses will be performed by fitting the Cox proportional hazard with a question indicator variable (one for each question, I and II) and adjusted by the stratification factors at randomization in the per protocol population.

8.2.4.2 Pre-planned exploratory analyses

In addition to the questions, pairwise comparisons of overall survival and progression-free survival between the three chemotherapy arms and the radiotherapy alone arm will be performed.

All comparisons will also be performed in each stratum of the following covariates: MGMT promoter methylation, 1p and 19q LOH and histological diagnosis. Factor or treatment by covariate interaction tests will be computed. Hazard Ratios with 99% confidence intervals will be tabulated. Forest Plots will be presented.

The distribution of MGMT promoter methylation status, 1p and 19q LOH in each histological diagnosis will be presented.

8.2.5 Prognostic factor analyses

Prognostic factor (PF) analyses for overall survival are prospectively planned. The main PF analysis will include: both questions (I and II), clinical covariates (WHO Performance Status, Age, Extent of Surgery, Tumor location, Previous surgery for Low Grade Glioma), Presence of oligodendroglial component, 1p/19q LOH status and MGMT promoter methylation status, histopathology parameters and biomarkers available at the time of analyses.

In the univariate stage, depending on its scale, each question and covariate will be screened by an appropriate two-sided logrank test (heterogeneity or trend). Kaplan-Meier curves will be computed. The Peto' interaction test will be computed between questions and between questions and covariates. Main effects and interactions with $p < 0.15$ will be considered for inclusion into the multivariate modeling stage. If an interaction is detected the main effects and interaction term will be included in the multivariate models. Variables will be included with their full categorization, no regrouping or selection of categories is allowed.

All selected covariates will be included into a multivariate Cox proportional hazards model. Both the automatic backward and stepwise selection method (significance to enter and/or stay in the model at 0.05) will be tested. The differences between the two selection methods will be documented. Nevertheless, in case of discrepancies, the selection of main effects and interactions provided by the stepwise selection method will be considered for the final model. As an internal validation, the bootstrap resampling technique will be used to estimate the probability of inclusion of each main effect or interaction term in Cox proportional hazards models with stepwise selection at 5% significance and identified the 10 models with the variables selected with the highest frequency. Only main effects or interactions with more than 60% probability of inclusion will be included in the final model.

If the final model of the main PF analysis includes interactions, additional models might be fitted in each question and/or chemotherapy arm separately applying the methodology described above.

The calibration, discrimination ability (Harrell's C-index) and Akaike's criteria (AIC) of final models will be estimated. Bootstrap technique will be used to correct parameters for "optimism" (Ref. 25).

Nomograms estimating individual patient's risk of progression or death before starting treatment and to predict medians and 2 years probabilities (other relevant endpoints might be considered) will be developed.

Proportional hazard assumptions will be checked by plotting the scale Schoenfeld residuals (Ref. 24) and by time-by-covariate interactions. If the data clearly do not follow proportional hazards, medical explanations should be identified and statistical solutions should be discussed with EORTC Applied Statistical Research group on non-proportional hazards models.

These analyses might be completed by analyses based on new techniques or methods available by the time of PF analyses.

8.2.6 Data recording and display

Frequency tables will be tabulated (by treatment group or otherwise) for all categorical variables by the levels of the variables as they appear on the CRF (with %). Categories with a text field specification will be tabulated as categories and then supplemented by a listing with the following information for the patients fulfilling the condition for the specification (patient id, institution, treatment group, value of the item and text field contents).

Dates relating to events prior to entry will be presented as the delay in days (or weeks, months, or years) between the past event and the date of entry (date of randomization – date of past event + 1) and presented using the median and range. For example, on the randomization checklist, the date of last administration of prior treatment (or the date of first diagnosis of the cancer) will be presented as the time elapsed (in days, weeks, months or years, as appropriate) since the day of the last administration and the date of entry on study (date of randomization – last administration/diagnosis +1). Other delays (e.g. re-treatment delays) are presented as continuous variables using the median and range.

Continuous variables for which a coding system exists (such as for laboratory data) will be recoded into categories (for adverse events, the grading scale specified in the protocol will be used). Whenever no specific scale exists, lab data will be categorized based on the normal range: for example, below the lower normal limit (when appropriate), within the normal range, above the upper normal limit (UNL) and the degree to which it is above the UNL (for example > 2.5 x UNL, > 5 x UNL, > 10 x UNL). For laboratory data, the nadir is generally displayed. The nadir in a given cycle is the lowest laboratory value in that cycle; the overall nadir for a patient is the lowest laboratory value among all cycles.

Other continuous variables (for example age, dose ...) will be presented using the median and range (minimum, maximum).

If appropriate, continuous data may also be presented in categories.

8.3 Interim analyses

8.3.1 Original plan

One formal interim analysis is planned for both questions when 219 events (41%) have been observed. Based on the assumption of the statistical design, the interim analysis should take place approximatively 4 years after the start of the trial when about 600 patients have been recruited.

Only the rejection of H_0 , the hypothesis of no efficacy, will be considered. Based on stopping boundaries from the Rho family ($Rho=2$), at the interim analysis, the nominal significance level for rejecting H_0 will be of 0.0084. The final analysis will be performed at a significance level of 0.0453. Power simulations were performed with EAST v 4.0.1.34 the results are presented in the table below based on 10000 simulations.

Scenario	Prob. of rejection of H0		Overall Power
	Interim analysis	Final analysis	
HR=0.63 (-ln(HR)=0.462)	79%	21%	99.9%
HR=0.775 (-ln(HR)=0.255)	23%	61%	83%
HR=0.80 (-ln(HR)=0.223)	16%	56%	72%
HR=0.825 (-ln(HR)=0.192)	11%	47%	59%

The probability of early stopping the assumption of the design is 23% at the interim analysis and 61% at the final analysis. The design still performs well if the true treatment effect is somewhat smaller than expected: for HR=0.80 the overall power is 72% with a 16% probability of early stopping at the interim analysis. For the pessimistic scenario of HR =0.825 the design will have a poor performance and the overall power will drop to 59%. Should the true difference between the treatment arms be comparable to the one observed in the EORTC 26981 (HR=0.63) trial, the probability of early stopping after the interim look increases to 79%.

The opportunity to stop the trial for futility (rejection of H1) was investigated. It was not possible to find a design allowing for rejection of H1 with sufficient power at an appropriate time of assessment before the end of the accrual period.

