8.1 Statistical design

8.1.1 Sample size

This is a 2 by 2 factorial design with Overall Survival as the primary endpoint when comparing:

- Patients receiving RT alone or RT + adjuvant TMZ to those receiving RT & concurrent TMZ or RT & concurrent TMZ + adjuvant TMZ.

[Question I: test for superiority of the concurrent TMZ chemotherapy]

- Patients receiving RT alone and RT & concurrent TMZ to those receiving RT + adjuvant TMZ or RT & concurrent TMZ + adjuvant TMZ.

[Question II: test for superiority of the adjuvant TMZ chemotherapy]

The hypotheses are the following:

- In the EORTC trial 26951 for Anaplastic Oligodendroglioma and Oligoastrocytoma tumors, patients with no combined 1p/19q LOH treated by RT alone had a median survival of 24 months. In the EORTC trial 26882 for Anaplastic Astrocytoma, patients treated by RT alone had a median survival of 24 months.
- No interaction is anticipated between the concurrent and adjuvant temozolomide treatment that are assumed to contribute equally to the survival improvement.
- In the EORTC trial 26981, comparing RT & Concurrent TMZ + adjuvant to RT alone, the estimated Hazard Ratio was 0.63 and its 95% Confidence Interval [0.52-0.75].

The following table summarizes the statistical parameters of the design. A Hazard Ratio (HR) of 0.775 is assumed for both questions.

RT		No adjuv CT (median OS)	Adjuv CT (median OS)	Question I	
				Median OS	HR
No conc CT		24 m	31 m	(24+31)/2=27.5	0.775
Conc CT		31 m	40 m	(31+40)/2=35.5	
Question II	Median OS	27.5	35.5		
	HR	0.775			

For both questions, to detect a reduction of the risk of death of 22.5%, based on a two-sided logrank test, at an overall significance level of 5% and a power of 83%, a total of 534 events are needed. With an estimated accrual rate of 150 patients per year, a total of **748** patients should be recruited within approximately 5 years. A minimum follow-up of 2 ½ years will be needed to observe the required number of events. One interim analysis for efficacy is planned when 41% of the events have been observed (219). To perform this interim look, 11 additional events are necessary. Power of the trial was slightly increased in order to compensate for the loss of information due to patients dropping out before starting the adjuvant treatment. It is estimated that 10% of the patients will fail during or within the month following radiotherapy.

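### Section 8.3.1 gives a 79% chance of early stopping for an effect like EORTC 26981, but that trial's combined HR of 0.63 implies about 0.794, and about 18%, per question

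*Combined protocol and SAP*

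**What the plan says.** Section 8.1.1 sets out the structure: "This is a 2 by 2 factorial design with Overall Survival as the primary endpoint when comparing" concurrent against no concurrent temozolomide (Question I) and adjuvant against no adjuvant temozolomide (Question II). The design effect is per question: "A Hazard Ratio (HR) of 0.775 is assumed for both questions". The two components are taken not to interact and are "assumed to contribute equally to the survival improvement".

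The same section describes the external evidence. In EORTC 26981, "comparing RT & Concurrent TMZ + adjuvant to RT alone, the estimated Hazard Ratio was 0.63", with a 95% confidence interval of 0.52 to 0.75. That contrast is both components against neither, which in this trial is arm 4 against arm 1.

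Section 8.3.1 plans one interim analysis for each question at 219 of 534 events, at nominal levels 0.0084 (interim) and 0.0453 (final). It tabulates rejection probabilities for HR 0.63, 0.775, 0.80 and 0.825. The text then takes up the case "Should the true difference between the treatment arms be comparable to the one observed in the EORTC 26981 (HR=0.63) trial" and says that the chance of stopping after the interim look rises to 79%. That is the interim figure in the table's 0.63 row, whose overall power is 99.9%.

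**The concern.** The table and the sentence use the same number, 0.63, for two different contrasts. In the table it is the effect of one component, because each row is a scenario for a single question. In EORTC 26981 it is the effect of two components given together. No section converts one into the other.

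The design table in 8.1.1 already shows the difficulty. It assumes a median survival of 24 months with radiotherapy alone and 40 months with both components, a combined HR of 24/40 = 0.60. An effect like that of EORTC 26981 (0.63) is therefore slightly weaker than the design assumption, so early stopping should be a little less likely than the design's 23%. The text says that it becomes much more likely.

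What is at stake is how the operating characteristics are read. A reader who takes the earlier trial as the best guide to the effect would expect a probable early stop where the plan's own assumptions do not support one.

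**Working it through.** **Inputs.** From 8.1.1: per-question design HR 0.775, two-sided 5% logrank test, 83% power, 534 events of which 11 are for the interim look, combined HR 0.63 (0.52 to 0.75), no interaction, equal contribution. From 8.3.1: 219 interim events, nominal levels 0.0084 and 0.0453. Equal allocation within each question is an assumption, since no ratio is stated; it reproduces the plan's figures.

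**Step 1: the design itself.**
- Fixed-design events (Schoenfeld): 4(1.960 + 0.954)² / (ln 0.775)² = 523, and 523 + 11 = 534.
- Rho = 2 spending at the interim: 0.05 × (219/534)² = 0.0084.
- Solving for the final boundary gives a nominal level of 0.0453.

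All three agree with the plan.

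**Step 2: the plan's table.** With d events the logrank statistic has mean (√d / 2) × (−ln HR).
- Interim rejection is Φ[(√219 / 2)(−ln HR) − 2.635], where 2.635 is the critical value for 0.0084.
- Overall power is the probability of crossing 2.635 at 219 events or 2.002 at 534 events, with correlation √(219/534) = 0.640.

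| HR | Interim / final / overall, recomputed (%) | Stated (%) |
|---|---|---|
| 0.63 | 78.3 / 21.6 / 99.96 | 79 / 21 / 99.9 |
| 0.775 | 22.7 / 60.4 / 83.0 | 23 / 61 / 83 |
| 0.80 | 16.2 / 56.0 / 72.2 | 16 / 56 / 72 |
| 0.825 | 11.3 / 48.1 / 59.3 | 11 / 47 / 59 |

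The agreement shows that every row, including 0.63, is a hazard ratio for one question.

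**Step 3: convert the EORTC 26981 effect.** With no interaction and equal contribution, combined HR = (per-question HR)².
- Combined 0.63 gives √0.63 = 0.794 per question.
- Design 0.775 per question gives 0.775² = 0.60 combined.
- A per-question HR of 0.63 would need 0.63² = 0.40 combined, outside the quoted interval of 0.52 to 0.75.

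**Step 4: operating characteristics at 0.794.**
- Interim mean: (√219 / 2) × 0.231 = 1.71. Rejection probability: Φ(1.71 − 2.635) = 17.7%.
- Rejection at the final analysis only: 57.5%. Overall power: 75.2% per question.
- At least one of the two questions crossing at the interim, treated as independent: 1 − (1 − 0.177)² = 32%.

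**Step 5: sensitivity.**
- The Freedman form gives 17.5% at the interim.
- A four-arm exponential simulation (748 patients, 150 per year, 24-month control median, 4,000 runs) gives 17.0% at the interim and 74.6% overall per question, and 31% for at least one question crossing.
- Across the EORTC 26981 interval, the per-question HR runs from √0.52 = 0.721 to √0.75 = 0.866. Interim rejection then runs from 41% to 6%, and overall power from 96% to 37%. No value in the interval gives 79% per question.

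**The case against.** The strongest reply is that the table is right and the realistic figures are already in it. This stands. The 0.63 row carries no reference to EORTC 26981 and is correct for a per-question HR. The rows for 0.80 (16% and 72%) and 0.775 (23% and 83%) bracket 0.794. The plan also discusses effects smaller than expected. The fault is confined to the sentence that names the earlier trial.

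A second reply is that one component might carry the whole effect. That question would then have HR 0.63 and the other HR 1.0. This contradicts the equal-contribution assumption, and the 79% would hold for one question only, which the text does not say.

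Four stronger readings are tempting, and the documents do not support them:

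- A reader might infer that the plan expressly promises 99.9% power if the earlier trial's effect holds. The sentence speaks only of early stopping; the 99.9% is reached by matching its HR to the table row.
- A reader might infer that the design is underpowered. Power of 75% at 0.794 against 83% at 0.775 is only what a weaker effect gives, as the table already shows.
- A reader might infer a defect in the new plan. Section 8.3.2 neither cites EORTC 26981 nor uses 0.63. Moreover, Question I had already passed the first look, so figures calculated from the start of the trial would not describe its position under that plan.
- A reader might infer that the monitoring committee relied on the 79%. Nothing in the documents shows this.

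**Conclusion.** The sentence in 8.3.1 is wrong in size and direction for the scenario it names. On the plan's own assumptions, an effect like that of EORTC 26981 gives about 18% interim rejection per question instead of 79%, below the design's 23%. Overall power is about 75% per question. The 18% is not a trial-level figure: the chance that at least one question crosses is about 32% under independence, still far from 79%.

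The result rests on no interaction and equal contribution on the log-hazard scale (both from 8.1.1), proportional hazards and equal allocation within each question. The normal approximation matters little, as the simulation shows.

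The spending function, boundaries, overall alpha, 534 events, 748 patients and 83% power at HR 0.775 are all unaffected. Section 8.3.2 records that the original interim has taken place, so this is a correction to the record and should be made as such.

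**What to change.** In 8.3.1, replace the sentence on EORTC 26981 with wording such as: If the combined effect equals that of EORTC 26981 (HR=0.63), the HR per question is about 0.794 under the design's no-interaction, equal-contribution assumption, with about 18% probability per question of rejecting H0 at the interim and about 75% overall power per question.

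Add a note to the table that its hazard ratios are per question, so that 0.63 there corresponds to a combined HR of about 0.40. The row can stay as it is, and a separate row for 0.794 is optional because 0.775 and 0.80 bracket it.

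The cost is one sentence and one note. No analysis, boundary or sample size changes; the only consequence is that the stated prospects for this scenario are less favourable.

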8.3.2 New plan

Further to the original interim analysis, the IDMC formulated the following recommendations:

- To release and publish the results on all endpoints for the adjuvant TMZ comparison without delay.
- In doing, so, to pay particular attention to the impact on patients in arms 1-2, who may benefit from initiating adjuvant TMZ and for whom a therapeutic decision to initiate such treatment may ensue. In particular, those patients who are still receiving RTX (with or without concomitant TMZ), as well as those patients who have finished RTX treatment within the past three months.
- To continue the follow-up for the concurrent TMZ question. Because of the very long follow-up time required to reach data maturity for overall survival for this question, consideration may be given to implementing a further interim analysis. The IDMC would welcome proposals for a revised plan incorporating a second such interim analysis.
- To take the necessary steps to obtain data on the MGMT promoter status for all patients, including reanalysis of samples using more modern assays that may require less material than the early assays. The investigators should assess heterogeneity of results across subgroups.

A new interim analysis plan was designed by an independent statistician. It includes an additional interim analysis for both efficacy and futility analysis at 2/3 of information (356 deaths) using the original spending function (stopping boundary from Rho family ($Rho=2$)) for the efficacy and an O'Brien Fleming stopping boundary for futility. This analysis will be binding in order to keep the same number of events and the 80% power at the final analysis. Based on these new assumptions, the trial will be stopped for futility if $HR \geq 0.882$ and for early efficacy if $HR < 0.778$. $HR=0.882$ corresponds to OS rate at 2 years of 71.9% in the no concurrent TMZ chemotherapy arm versus 74.7% in the concurrent TMZ chemotherapy arm (less than 3% difference observed). The timing of this second interim analysis is at about 35 months after end of accrual i.e. September 2018. The final analysis is expected in 2022 at will be performed at a significance level of 0.044 ($HR < 0.841$).

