Objective(s)	
This trial is a follow up study of EORTC 26981 and of EORTC 26951 addressing the overall strategy of optimizing the treatment in newly diagnosed anaplastic glioma patients without combined 1p/19q loss. Patients will be randomized immediately after surgery to one of the four following therapeutic options:
 
Arm 1 : RT alone (and further treatment including chemotherapy at progression) Arm 2 : RT & concurrent CT Arm 3 : RT + adjuvant CT Arm 4 : RT & concurrent CT + adjuvant CT
 
Twelve months of adjuvant treatment is foreseen. Patients will be included based on the 1p/19q status of the tumor. Centers with known expertise in 1p/19q testing will be allowed to include patients based on local testing, with central review for 1p/19q testing (and histology). For sites without access to 1p/19q testing a central facility will be created. Methylation status of the MGMT promoter gene will be a stratification factor.
 
Primary objectives:
 
To assess whether concurrent radiotherapy with daily temozolomide chemotherapy improves overall survival as compared to no daily temozolomide in non-1p/19q deleted anaplastic glioma.
 
To assess whether adjuvant temozolomide chemotherapy improves survival as compared to no adjuvant temozolomide chemotherapy in non-1p/19q deleted anaplastic glioma

Methodology	Phase III – difference
Number of patients Number planned (Statistical design) Number analyzed	
This is a 2 by 2 factorial design with Overall Survival as the primary endpoint when comparing:
 
Patients receiving RT alone or RT + adjuvant TMZ to those receiving RT & concurrent TMZ or RT & concurrent TMZ + adjuvant TMZ.
 
[Comparison I]: test for superiority of the concurrent TMZ chemotherapy]
 
Patients receiving RT alone and RT & concurrent TMZ to those receiving RT + adjuvant TMZ or RT & concurrent TMZ + adjuvant TMZ.
 
[Comparison II]: test for superiority of the adjuvant TMZ chemotherapy]
 
For both comparisons, to detect a reduction of the risk of death of 22.5% based on a two-sided logrank test, at an overall significance level of 5% and a power of 83%, a total of 534 events are needed. With an estimated accrual rate of 150 patients per year, a total of 748 patients can be recruited in 5 years. A minimum follow-up of 2 ½ years will be needed to

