	
observe the events. One interim analysis for efficacy only is planned when 41% of the events have been observed (219). To perform this interim look 11 additional events were necessary to preserve the study power.

Diagnosis and main criteria for inclusion
	
Histologically confirmed newly diagnosed anaplastic oligodendroglioma, anaplastic oligoastrocytoma or anaplastic astrocytoma by local diagnosis and absence of combined 1p/19q loss
 
Availability of tumor material for central 1p/19q assessment, central MGMT promoter methylation assessment and central pathology review
 
Previous surgery for a low grade tumor is allowed, provided histological confirmation of an anaplastic tumor is present at the time of progression
 
WHO performance status 0-2
 
Age \geq 18 years
 
Start of radiotherapy within 8 days from randomization
 
Start of radiotherapy within 7 weeks (49 days) from surgery
 
No prior chemotherapy
 
No prior radiotherapy to the brain

Treatment
 
Test product, dose and mode of administration
	
Radiotherapy (arms 1-4)
 
Radiotherapy will consist of a conventionally fractionated regimen, delivering a total dose of 59.4 Gy in 6.5 weeks, in a once daily schedule of 1.8 Gy per fraction for a total of 33 fractions.
 
Concomitant temozolomide (arms 2 & 4)
 
Patients randomized to concomitant temozolomide will receive temozolomide continuously at a daily dose of 75 mg/m² during radiotherapy. The drug will be administered orally 1 hour before each session of radiotherapy during weekdays. During weekends without radiotherapy, the drug will be taken in the morning. The dose administered will be determined using the body surface area (BSA) calculated at the beginning of the concomitant treatment. The daily dose will be rounded to the nearest 5 mg.
 
Adjuvant temozolomide (arms 3 & 4)
 
Patients randomized to adjuvant temozolomide will start adjuvant temozolomide after a 4 week resting period after the end of radiotherapy. Temozolomide will then be administered orally once a day for 5 consecutive days (days 1-5). The starting dose for the first cycle will be 150 mg/m²/day with a single dose escalation to 200mg/m²/day in subsequent cycles if no significant toxicity is observed in the first cycle. The dose administered will be determined using the BSA calculated at the beginning of each treatment cycle. The dose will be rounded to the nearest 5 mg.

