8.2.3.2 Analyses methods for efficacy endpoints

For the primary analysis of overall survival and progression-free survival, the Cox proportional hazards model will be fitted with a question indicator variable (one for each question, I and II) and adjusted by the stratification factors at randomization. For overall survival the nominal significance level to be used at the interim look and final analysis is described in section 8.3 below.

In the final report, important secondary analyses of overall survival will be 1) the Cox models with adjustment of the questions by MGMT promoter methylation status after randomization and the other stratification factors. 2) the Cox models with adjustment of the questions by IDH1 mutation status (in replacement of MGMT promoter methylation status) and the other stratification factors. Significance level used for these two secondary analyses is the same as for the primary analysis. All analyses of progression free survival will be performed at a 5% significance.

The Kaplan-Meier technique will be used to obtain estimates of the overall survival and progression-free survival. The hazard ratios will be estimated with their 95% confidence intervals. Medians will be presented with 95% confidence interval provided by the Reflected Method (Ref. 23). 5 year survival and progression-free survival rates will be presented with 95% confidence interval calculated by Greenwood formula's estimation of the standard deviation.

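### Question I: the synopsis and 8.1.1 still give the one-look plan with 83% power, and in 8.3.2 the final level 0.044 does not match HR < 0.841

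*Combined protocol and SAP*

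**What the plan says.** The synopsis (number of patients) and section 8.1.1 size the trial for both questions with the same statement: "at an overall significance level of 5% and a power of 83%, a total of 534 events are needed". On monitoring, the synopsis says "One interim analysis for efficacy only is planned when 41% of the events have been observed (219"), and 8.1.1 says "One interim analysis for efficacy is planned when 41% of the events have been observed (219"). Neither mentions a second look, a futility rule or 80% power.

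Section 8.3.1, headed as the original plan, gives nominal levels of 0.0084 at the interim and 0.0453 at the final analysis.

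Section 8.3.2, headed as the new plan, follows the data monitoring committee's recommendation to continue follow-up for the concurrent question. It adds a look at 356 deaths, "using the original spending function (stopping boundary from Rho family ($Rho=2$)) for the efficacy" and an O'Brien-Fleming boundary for futility. The limits at that look are HR 0.882 or above for futility and HR below 0.778 for efficacy. On power it says "This analysis will be binding in order to keep the same number of events and the 80% power at the final analysis". The final analysis is then "performed at a significance level of 0.044 ($HR < 0.841").

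Section 8.2.3.2 sends the reader to the boundaries with "For overall survival the nominal significance level to be used at the interim look and final analysis is described in section 8.3 below".

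**The concern.** Two things do not fit together.

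- **Power and looks.** The synopsis and 8.1.1 describe a plan that no longer applies to Question I. The synopsis's restriction to efficacy is no longer true for that question, and the power it gives is higher than the figure in 8.3.2. Section 8.2.3.2 speaks of one interim look and points to 8.3 as a whole, which holds two plans with different final levels (0.0453 and 0.044).
- **Final success rule.** In 8.3.2 the significance level and the hazard ratio are printed as one cut-off, but at 534 deaths they are not. A final hazard ratio between 0.840 and 0.841 would meet one and miss the other.

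At stake are the stated power and the final decision rule for the primary question that remains open.

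**Working it through.** **Inputs.** Target HR 0.775, 534 deaths, two-sided 5% (8.1.1). First look at 219 deaths, Rho = 2 (8.3.1). Second look at 356 deaths, same spending function, binding futility at HR 0.882 (8.3.2). Assumptions: deaths split 1:1 within each factorial margin; spending of 0.025·t² per side; log-HR variance 4/d, so z = −ln(HR)·√d/2 and HR = exp(−2z/√d). Boundaries and power come from recursive numerical integration with information d/4.

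**1. Original plan.**
- Schoenfeld events at 83% power: 4(1.960 + 0.954)²/(ln 0.775)² = 523; adding the stated 11 gives 534, as printed.
- First look: 0.025 × (219/534)² = 0.00420 per side, so p = 0.0084, as printed.
- Power with levels 0.0084 and 0.0453: 83.0% at HR 0.775 and 72.2% at HR 0.80, as printed in 8.3.1 (83% and 72%).

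The 83% is therefore correct for the one-look plan.

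**2. New plan.**

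| Look | One-sided alpha spent at this look | z | Two-sided p | HR | Printed |
|---|---|---|---|---|---|
| 219 | 0.00420 | 2.635 | 0.0084 | 0.700 | p 0.0084 |
| 356, efficacy | 0.00691 | 2.372 | 0.0177 | 0.7776 | HR 0.778 |
| 356, futility | – | 1.185 | – | 0.882 | HR 0.882 |
| 534 | 0.01389 | 2.005 | 0.0450 | 0.8407 | p 0.044, HR 0.841 |

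Power at HR 0.775 is 0.227 + 0.300 + 0.279 = 80.7%, in line with the stated 80%. Solving the O'Brien-Fleming futility bound with beta set to one minus the achieved power gives a futility limit of HR 0.8821 (printed 0.882) and a final level of 0.044996. Of the 8.3.2 boundary and power figures checked, only 0.044 fails to reproduce.

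**3. The printed pair at 534 deaths (√534 = 23.108).**
- p 0.044: z = 2.014, HR = exp(−2 × 2.014/23.108) = 0.8400.
- HR 0.841: z = 0.17316 × 23.108/2 = 2.001, p = 0.0454.
- Rounding to the nearest does not reconcile them. A level of 0.0435 to 0.0445 corresponds to HR 0.8397 to 0.8404; HR 0.8405 to 0.8415 corresponds to p 0.0447 to 0.0462.

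**4. Consequences of each final rule, with the binding stop.**

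| Final rule | One-sided alpha | Power, HR 0.775 | Power, HR 0.80 |
|---|---|---|---|
| p 0.044 | 2.47% | 80.5% | 69.4% |
| p 0.0450 | 2.50% | 80.7% | 69.7% |
| HR 0.841 | 2.51% | 80.7% | 69.7% |

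The chance of landing between the two printed cut-offs is 0.02513 − 0.02466 = 0.05% under no effect and 0.8075 − 0.8052 = 0.23% at HR 0.775. A simulation of 4 million trials agrees: power 0.8052 at 0.044 and 0.8067 at 0.0450, with one-sided alpha 0.0247 and 0.0250.

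**5. Could another reading give 0.044?**
- Futility limit over its rounding range (HR 0.8815 to 0.8825), or 0.778 taken as the second-look limit: final level 0.0449 to 0.0451.
- Non-binding futility: 0.0390 with HR 0.836, which matches neither printed figure.
- Leaving out the 219-death look: second-look efficacy limit HR 0.785, which contradicts 0.778.
- A level of 0.044 needs a futility limit near HR 0.887.
- Moving the second look to 360 deaths gives about 0.0446, with HR 0.840.

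**The case against.** The strongest reply is that nothing is miscalculated in substance. The 83% is right for the design that fixed 534 deaths and 748 patients, and it still describes Question II, which has no second look. Section 8.3.2 prints 80%, and the two subsections of 8.3 are clearly labelled, so a reader sent there can find the plan in force. Section 8.1.1 also keeps its initial registration assumptions and adds the later update after them.

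On the final rule, 8.2.3.2 speaks of a nominal significance level and 8.3.2 gives the HR only in brackets, so the level already governs. The primary test is an adjusted Cox model, in which a p-value does not fix one HR. The computed level of about 0.045 sits on a rounding edge: 0.044996 cut to three decimals prints as 0.044, and 0.8407 rounds to 0.841. The pair could come from one coherent output with one truncated digit. Using 0.044 is also slightly conservative.

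Much of this stands. The power calculations are each correct for their own plan, truncation is a plausible explanation, and the numerical effect is very small. But truncation would explain 0.044 without making it the level that the stated boundaries give, or the equivalent of HR 0.841. And no pointer in the synopsis or 8.1.1 tells the reader that the monitoring plan and power have changed for Question I.

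**Conclusion.** The concern holds. For Question I the synopsis and 8.1.1 are out of date: power at HR 0.775 is 80.5% to 80.7%, not 83%, and there are two interim looks, the second with binding futility. In 8.3.2 the final level and HR do not match, and 0.044 is the outlier; the stated design gives 0.0450 with HR 0.8407. The outdated text is the larger part. The mismatch costs at most about 0.2 points of power and leaves one-sided alpha between 2.47% and 2.51%.

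This rests on a 1:1 split of deaths, looks at exactly 219, 356 and 534 deaths, and the 4/d variance. The adjusted Cox model may shift the HR equivalents slightly. The design output is not in the documents, so the reason for 0.044 cannot be settled from them.

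**What to change.** - **Synopsis and 8.1.1:** for Question I, list both looks (219 deaths, efficacy; 356 deaths, efficacy and binding futility) and state power of about 80%. Identify 83% as the original-plan figure.
- **8.2.3.2:** for Question I, refer to 8.3.2 and to both interim looks.
- **8.3.2:** confirm the final level from the design output and print one matching pair. State that the significance level governs and that the HR is its approximate equivalent at 534 deaths. By calculation the pair is 0.045 with HR about 0.841. If 0.044 is kept deliberately, the matching figure is HR < 0.840.

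The cost is text changes in four places and one check of the design output, with no extra patients or deaths. Keeping 0.044 instead of 0.045 costs about 0.2 points of power (80.5% against 80.7%).
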